6.1 Analysis Sets

6.1.1 Enrolled Subjects

A subject is considered to be enrolled in the study if he/she has provided informed consent.

6.1.2 Pharmacokinetic Analysis Set

The Pharmacokinetic Analysis Set is the group of subjects who dosed with the test drug and had sufficient PK data to derive at least 1 PK parameter.

6.1.3 Safety Analysis Set

The Safety Analysis Set is the group of subjects who dosed with the test drug and had at least 1 postdose safety assessment.

6.2 Derived Data

This section describes the derivations required for statistical analysis. Unless otherwise stated, variables derived in the source data will not be re-calculated.

6.2.1 Race

Where more than one race category has been selected for a subject, these race categories will be combined into a single category labeled "Multiple" in the summary tables. The listings will reflect the original selected categories.

6.2.2 MELD Score

The MELD score at Screening for each subject (in each of the three cohorts) will be calculated as follows per the OPTN policy, January 2016 (pages 4-5)²:

First the initial MELD score will be calculated:

 $MELD(i) = [0.957 \times log_e(Creatinine)] + [0.378 \times log_e(bilirubin)] + [1.120 \times log_e(INR)] + 0.643$

This value will be rounded to two decimal places and multiplied by 10.

If calculated value for MELD(i) is > 11, the additional MELD calculation will be performed:

 $MELD = MELD(i) + [1.32 \times (137 - Serum Sodium)] - [0.033 \times MELD(i) \times (137 - Serum Sodium)]$

This recalculated MELD value will be rounded to the nearest integer. If $MELD(i) \le 11$ then the recalculated MELD value will equal the initial MELD value.

The following scheduled screening values are used:

- Creatinine in mg/dL
- Bilirubin in mg/dL
- INR
- Sodium in mmol/L

Where the scheduled screening value is missing the first non-missing repeat scheduled value will be used.

The following additional rules will be followed:

- If the Bilirubin, Creatinine, or INR value is <1.0 a value of 1.0 will be used in the calculation.
- If Creatinine>4.0 mg/dL, a value of 4.0 will be used in the calculation
- If Sodium <125 mmol/L, a value of 125 will be used in the calculation.
- If Sodium >137 mmol/L a value of 137 will be used in the calculation.

The maximum MELD score is 40.

6.2.3 Pharmacokinetic Parameters

Concentration time data for lemborexant and its metabolites will be provided following database lock and will be analyzed by non-compartmental methods using Phoenix[™] WinNonlin[®] (Version 6.3 or later, Pharsight Corporation), in accordance with Eisai 302-104.00-MNL Non-Compartmental Pharmacokinetic Analysis (effective date 08 Jun 2016).

Concentrations that are below the limit of quantification (BLQ) will be treated in accordance with Section 2.5.1 of Eisai 302-104.00-MNL. During the pharmacokinetic analysis, BLQ values at predose up to the first quantifiable concentration will be set to zero; BLQ values between 2 quantifiable concentrations will be set to "missing"; and quantifiable concentrations preceded by 2 or more consecutive BLQ values in the terminal phase will be set to missing.

The following PK parameters will be calculated for lemborexant and its metabolites (as data permit):

C _{max}	Maximum plasma concentration determined directly from individual concentration-time data, reported to 3 significant figures
t _{max}	Time to reach maximum plasma concentration determined directly from individual concentration-time data, reported to 2 decimal places
AUC ₍₀₋₇₂₎	Area under the plasma concentration-time curve from time zero to 72 hours postdose; calculated using the linear-log trapezoidal rule (linear-up log-down), reported to 3 significant figures
AUC(0-t)	Area under the plasma concentration-time curve from time zero to the time of the last quantifiable concentration; calculated using the linear-log trapezoidal rule (linear-up log-down), reported to 3 significant figures

AUC(0-inf)	Area under the plasma concentration-time curve extrapolated to infinity, reported to 3 significant figures and calculated as:
	$AUC_{(0-inf)} = AUC_{(0-t)} + C_{last}/\lambda z$
AUC _{ex}	The percentage of AUC_{0-inf} based on extrapolation, reported to 3 significant figures and calculated as:
	$AUC_{ex} = (AUC_{(0-inf)} - AUC_{(0-i)})/AUC_{(0-inf)}*100$
t _{1/2}	The observed terminal elimination half-life, calculated as: $t_{1/2} = \ln(2)/\lambda_z$; see additional criteria below, reported to 3 significant figures
λ_z	The observed elimination rate constant; estimated by linear regression through at least three data points (not including t_{max}) in the terminal phase of the log concentration-time profile; see additional criteria below, reported to 3 significant figures
CL/F Vz/F	Apparent body clearance, reported to 3 significant figures and calculated as: $CL/F = Dose/AUC_{(0-inf)}$; calculated for lemborexant only Apparent volume of distribution based on the terminal phase, reported to 3 significant figures and calculated as: $Dose/(\lambda_z \times AUC_{(0-inf)})$; calculated for lemborexant only
MPR AUC(0-inf)	Ratio of $AUC_{(0-inf)}$ of individual metabolite to $AUC_{(0-inf)}$ of lemborexant, corrected for molecular weights, reported to 3 significant figures
fu	plasma protein unbound fraction, reported to 3 significant figures
AUCu	AUC _(0-inf) values adjusted by unbound fraction in plasma, reported to 3 significant figures; calculated for lemborexant only
CLu/F	Apparent clearance relative to the unbound plasma concentration based on AUCu, reported to 3 significant figures (for lemborexant only)

At least 3 time points with quantifiable plasma concentrations will be required for the calculation of AUC_(0-t). Individual AUC_(0-inf) values for which AUC_{ex} >20% will be retained in the end of text tables and will not be included in the summary statistics. Individual AUC_(0-inf) values for which AUC_{ex} >20% may be included in the summary statistics if approved by the Sponsor.

At least 3 time points (of which the first time point must be greater than t_{max}) with quantifiable plasma concentrations will be required for the calculation of λz .

No value for λ_z and other λ_z -related parameters (AUC_(0-inf), t_{1/2}, CL/F, etc.) will be reported for lemborexant and its metabolites if the PK Analyst or the Sponsor decides a reliable estimate of λ_z is not possible after considering the following factors:

- 1) The duration of time over which λ_z is estimated (λ_z range) is less than twice the subsequently estimated terminal elimination phase half-life ($t_{\frac{1}{2}}$).
- 2) The adjusted regression coefficient (R^2 adj) is not ≥ 0.90 ; and
- 3) The concentration profiles do not exhibit a terminal elimination phase in the concentration versus time profile.
- 4) If the % extrapolation is > 20, related parameters AUC_(0-inf), CL/F, and Vz/F will be reported based on the pharmacokineticist's judgment.

6.2.4 Baseline

Baseline for the safety variables is defined as the last non missing value (either scheduled, unscheduled or repeat) before the subject receives the dose of lemborexant on Day 1. For laboratory variables only results provided by the Worldwide Clinical Trials laboratory will be used as baseline values.

6.2.5 Duration/Study Day/Time

Study day will be calculated as the number of days from the dose of lemborexant on Day 1 using the following rules:

- date of event date of first dose + 1, for events on or after first dose
- date of event date of first dose, for events before first dose.

6.2.6 Conventions for Missing and Partial Dates

All dates presented in the individual subject listings will be as recorded on the electronic case report form (eCRF).

6.2.7 Unscheduled Visits

Only scheduled post baseline laboratory and vital signs values will be tabulated. Post baseline repeat/unscheduled assessments will be disregarded unless otherwise stated, although these post baseline assessments will be listed in Appendix 16.2.

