9.5.2.2 Total Volume of Blood Sampling

Table 6 presents the number of blood samples and the total volume of blood that will be collected throughout the study. Additional samples may be taken at the discretion of the investigator if the results of any tests fall outside reference ranges or clinical symptoms necessitate testing to ensure subject safety.

Table 6	Summary of Blood Sample Volumes
---------	---------------------------------

	Sample Volume per Collection (mL)	Number of Collection Time Points	Total Volume Collected (mL)
Clinical laboratory tests	8.5	Screening (including pregnancy testing): 1 Baseline (Day -1): 1 Day 2: 1 Day 14 or early termination: 1	8.5×4=34
Viral test	8.5	Screening: 1	8.5×1=8.5
PK blood sampling	4	20	4×20=80
Blood sampling for plasma protein binding	12	2	2×12=24
Total			146.5

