6.17.2 Laboratory Data

Laboratory data at Day -1 was analyzed by both a local laboratory and Worldwide Clinical Trials laboratory. Data from both laboratories will be listed but summary tables will only include data provided by Worldwide Clinical Trials.

All laboratory data will be listed and summarized using the International System of Units (SI). For continuous variables descriptive statistics of the observed values and change from baseline will be presented by cohort at each scheduled assessment and Early Termination (if applicable) for each hematology, serum chemistry, urinalysis, and coagulation parameter. For categorical variables the number and percentage of subjects in each reported level will be presented. Each hematology, serum chemistry, and urinalysis measurement will be classed as below, within, or above normal range, based on ranges supplied by the laboratory used. Shift tables in relation to the normal range from baseline to each post baseline assessment and Early Termination (if applicable) will be presented.

A listing of any markedly abnormal laboratory measurements (defined as meeting the criteria for grade 2 or higher in the sponsors grading of laboratory values presented in Appendix 1 to the study protocol) that were recorded throughout the study will be presented. The incidence of markedly abnormal laboratory results over the course of the study will be listed.

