6.17.3 Vital Signs

Descriptive statistics of the observed values and change from baseline will be presented by cohort and timepoint for the following:

- Systolic blood pressure (mmHg)
- Diastolic blood pressure (mmHg)
- Pulse rate (bpm)
- Respiration Rate (breaths/min)
- Body Temperature (degrees Celsius)

The incidence of subjects reporting an increase or decrease greater than 20mmHg in systolic or 15 mmHg in diastolic blood pressure relative to baseline will be summarized at each post baseline assessment.

Weight at Day -1 will be listed only.

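### A repeat can serve as safety baseline but post-dose repeats are not tabulated, so changes and shifts can show spurious worsening near a limit, and unscheduled post-dose blood pressures go uncounted

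*SAP*

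**What the plan says.** **Before dosing.** SAP 6.2.4 defines the safety baseline as "the last non missing value (either scheduled, unscheduled or repeat) before the subject receives the dose of lemborexant on Day 1". For laboratory data it adds a limit on source: "For laboratory variables only results provided by the Worldwide Clinical Trials laboratory will be used as baseline values". The limit matters because, according to SAP 6.17.2, "Laboratory data at Day -1 was analyzed by both a local laboratory and Worldwide Clinical Trials laboratory".

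**After dosing.** SAP 6.2.7 states: "Only scheduled post baseline laboratory and vital signs values will be tabulated". Repeats are then set aside: "Post baseline repeat/unscheduled assessments will be disregarded unless otherwise stated". They are kept in the Appendix 16.2 listings. Neither SAP 6.17.2 (laboratory changes and shift tables) nor 6.17.3 (vital-sign changes and blood pressure threshold counts) states an exception. The addendum of 24 July 2018 does not touch these rules.

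**What can trigger a repeat.** Protocol 9.5.2.2 says: "Additional samples may be taken at the discretion of the investigator if the results of any tests fall outside reference ranges". Clinical symptoms are the other trigger named there.

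**Blood pressure.** SAP 6.17.3 counts subjects with an "increase or decrease greater than 20mmHg in systolic or 15 mmHg in diastolic blood pressure relative to baseline" at each post-baseline assessment. Protocol Table 4, footnote b, schedules vital signs on Day 1 at predose only, and next on Day 2. Protocol 7.1.1.2 puts peak plasma concentration at around 1 to 3 hours after dosing.

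**The concern.** The two sides of each change score follow different selection rules, and the SAP gives no reason. If repeats were taken at random this would not matter. But an out-of-range result is one of the named reasons for taking another sample. Eligibility is also checked again on Day -1, including the QTc and creatinine clearance criteria, which gives a site a reason to re-test an abnormal value shortly before dosing. A high pre-dose value can then be replaced by its repeat, which tends to be lower, while an equally high post-dose value stands. In a subject whose true value is near the limit, the tables would lean toward normal-to-high shifts with no drug effect at all.

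At stake are the laboratory change tables (with the 95% confidence limits for mean change that SAP 6.3 asks for), the laboratory shift tables and, to a lesser degree, the vital-sign tables. With 8 subjects per cohort, one spurious shift is 12.5% of the cohort.

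The second issue is separate and runs the other way. A blood pressure taken because a subject feels faint near peak concentration is by definition unscheduled, so the threshold incidence cannot show it.

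**Working it through.** The documents give no figure on this point. Their one precision figure, 1.645 × 0.391 × √(1/8 + 1/8) = 0.322, concerns the AUC(0-inf) comparison and is not an input here.

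**Assumptions (none is given in the documents).** No true change; normal within-subject variation with SD s; an upper limit L; true mean μ, with z = (L − μ)/s; at most one repeat of a value above L, taken with probability r and used as baseline.

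**Formulas.** Let p = Φ(z), the chance that a single reading is within the limit.
- Expected baseline = μ − r·s·φ(z). The scheduled post-dose value has mean μ, so the spurious mean change is r·s·φ(z).
- With r = 1, the baseline is normal with probability p + (1 − p)p = p(2 − p). Normal-to-high shifts are then p(2 − p)(1 − p), and high-to-normal shifts are p(1 − p)².
- For any r, the excess of normal-to-high over high-to-normal is r·p(1 − p).
- If scheduled values are used on both sides, each direction is p(1 − p) and the mean change is 0.

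**Results for r = 1.**

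| z | p | Spurious mean change | Normal-to-high | High-to-normal | Scheduled-only, each way |
|---|---|---|---|---|---|
| 0 | 0.500 | 0.40 s | 37.5% | 12.5% | 25.0% |
| 0.5 | 0.691 | 0.35 s | 27.9% | 6.6% | 21.3% |
| 1 | 0.841 | 0.24 s | 15.5% | 2.1% | 13.3% |
| 2 | 0.977 | 0.05 s | 2.3% | 0.05% | 2.2% |

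Both φ(z) and p(1 − p) are largest at z = 0, so the first row is the upper bound of this model. Simulation with 2,000,000 draws per setting agrees. Using repeats on both sides would also balance the table, at 0.75 × 0.25 = 18.8% each way at the limit; the scheduled-only rule gives 25% each way.

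**Range over repeat rates.** For z from 0 to 2 and r from 0.25 to 1, the excess runs from 0.25 × 0.022 = 0.6 points to 25 points, and the mean change from about 0.01 s to 0.40 s.

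**Whole cohort (simulated; intraclass correlation 0.5 to 0.8, r from 0.25 to 1).**
- Limit 1.96 total SD above the cohort mean: excess 0.4 to 2.0 points, or 0.03 to 0.16 of 8 subjects per parameter and visit.
- Limit 1 total SD above the mean: 1.5 to 9.6 points, or 0.12 to 0.77 of 8 subjects.

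**When the bias disappears or changes form.** If repeats are unrelated to the result, shifts balance (21.3% each way at z = 0.5) and the mean change is 0. With limits on both sides and a mid-range subject (limits 1.96 s away, r = 1), the mean change is about 0, but high-to-normal shifts are still under-counted (0.1% against 2.5% normal-to-high).

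**Blood pressure coverage.** Scheduled vital signs run from Day 1 predose to Day 2, then Days 8, 10, 12 and 14. Peak concentration falls between the first two. Every reading taken in that gap is unscheduled and is excluded by SAP 6.2.7.

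**The case against.** The strongest reply is that the conditions for the bias will seldom be met. Most of it stands.

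- **The window is short.** A repeat counts only if it is the last value before dosing. Screening re-tests are superseded by the Day -1 laboratory sample and by the Day 1 predose vital signs and ECG. A laboratory repeat would have to fall between the Day -1 sample and the morning dose, and a re-test analysed only locally cannot become baseline.
- **Repeats are discretionary.** The protocol permits extra samples and does not require them. The r = 1 figures are a ceiling, and no repeat rate is given.
- **No repeat trigger is documented for blood pressure.** Protocol 9.5.2.2 concerns samples, and Table 4 calls for single vital-sign measurements. Carrying the baseline bias over to the >20/>15 mmHg count is inference, and since that count takes changes in either direction, worsening has no defined sign there.
- **The data remain visible.** Post-baseline repeats are listed, as are markedly abnormal laboratory results from throughout the study. With about 24 subjects each can be inspected. The safety tables are descriptive.
- **The last pre-dose value is a coherent baseline choice**, being closest to the dose.

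Listings do not correct a table, however, and none of these points explains why the rule differs before and after dosing.

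A reader might also infer that the artefact falls harder on the hepatically impaired cohorts, because they sit nearer the laboratory limits, and so distorts the comparison with controls. The documents do not support this. Abnormal albumin or bilirubin contributes to the Child-Pugh score that qualifies an impaired subject, so there may be less reason to repeat it. Healthy subjects are excluded for abnormal liver tests or findings that need follow-up (criteria 33 and 35), so re-testing could be commoner among controls.

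**Conclusion.** The asymmetry is real, and where a pre-dose repeat is prompted by an abnormal result its direction is toward apparent worsening near that limit. It arises only if that repeat is the last value before dosing and, for laboratory data, comes from the named laboratory. Subjects without such a repeat are compared like with like.

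The ceiling is 0.40 within-subject SD and 37.5% against 12.5% shifts, assuming normal variation, no true change, a true value at the limit and a repeat of every out-of-range value. Across a cohort the simulated excess is below one subject in 8 per parameter and visit, before allowing for the short window. The actual effect is therefore probably small. It would be wrong to read the plan as certain to produce false worsening, or as biased in one direction overall, because excluding unscheduled post-dose readings can also hide real worsening. A difference between cohorts is not established, and the primary PK analysis is unaffected.

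The blood pressure point does not depend on the repeat model. As written, the >20/>15 mmHg incidence cannot include any reading between the Day 1 predose measurement and Day 2.

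This is a cheap improvement to the safety tables and does not threaten the study's conclusions.

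**What to change.** 1. In SAP 6.2.4 and 6.2.7 state one selection rule for both sides of the dose. For example, use the last scheduled pre-dose value as baseline and the scheduled value at each later visit, with a repeat only where the scheduled result is missing or documented as invalid. SAP 6.2.2 already takes the scheduled value first, and a repeat only if it is missing, for the MELD inputs; the allowance for invalid results would be new. If the sponsor prefers the last value, it should apply on both sides.
2. In the same edit, say whether 6.2.7 covers the ECG shift table, since its opening sentence names only laboratory and vital-sign values.
3. In SAP 6.17.3 add one row to the blood pressure incidence, clearly labelled as any post-baseline value including unscheduled readings.

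**Cost.** SAP wording and minor reprogramming, with no new data. A few baselines may revert from a repeat to the scheduled reading. The added row will reflect symptom-driven measurement, so its label should say so and it should not be compared with the by-visit rows. If the tables already exist, the new versions can be reported as additional tables with their justification, which SAP section 6 allows.

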6.2.8 Potential Cataplexy AEs

Potential AEs of Cataplexy are identified as those AEs with a verbatim term coded to one of the following MedDRA preferred terms:

Cataplexy	Dysarthria	Apallic syndrome	Presyncope
Margala fations		Consciousness	Transient ischaemic
Muscle latigue	Slow speech	fluctuating	attack
M	Heteronymous	Depressed level of consciousness Amaurosis fugax	
Muscular weakness	diplopia		
Mugaulan tana digandan		Latharay	Capsular warning
Muscular tone disorder	Homonymous diplopia	Lethargy	syndrome
Hernotonio		Loss of consciousness	Reversible ischaemic
Hypotonia	Eyelid myoclonus	LOSS OF CONSCIOUSILESS	neurological deficit
Drop attack	Myoclonus	Sopor	
Slurred speech	Opsoclonus myoclonus	Stupor	
Dintenie	Clanus	Transient global	
Dipiopia	Cionus	amnesia	
Falls	Altered state of	Suncene	
Fails	consciousness	Syncope	

Such AEs are identified on the eCRF by an answer of 'Yes' to the question 'Potential Cataplexy AE?'.

6.3 Conventions

All data listings, summaries, figures and statistical analyses will be generated using SAS¹ version 9.4 or higher or Phoenix[™] WinNonlin[®] (Version 6.3 or later, Pharsight Corporation).

Listings will be sorted in the following order: cohort (Child Pugh Class A, Child Pugh Class B, followed by Healthy Subject cohort), subject, parameter, and day, unless otherwise stated. All data will be listed.

Continuous variables will be summarized by the number of non missing observations, mean, median, standard deviation (SD), and minimum and maximum. For all tabulations of changes from baseline data, the lower and upper 95% confidence limits for the mean for the individual treatments will be given. In addition PK parameter data will have the geometric mean and coefficient variation (CV%) presented. CV% will be calculated as sqrt(exp[SD² of log transformed data]-1)*100.

Categorical variables will be summarized by presenting the frequency and percent. Percentages will be based on the number of non missing observations or the subject population unless otherwise specified. For each variable, all categories will be shown. Zero frequencies (but not the percent) within a category will be presented.

6.3.1 Decimal Places

For pharmacokinetic data, when presenting individual/raw (raw, hereafter) values and summary statistics, the following rules will be applied: for drug concentrations and concentration-dependent pharmacokinetic parameters, all summary statistics (mean, median, geometric mean, SD, and CV%) will have 3 significant digits. For t_{max}, raw values and summary statistics will be presented to 2 decimal places.

The adjusted regression coefficient (R^2 adj) will be presented to 3 significant digits. The number of time points used in the lambda-z estimates will be presented as an integer number. Lower and upper times of the lambda-z range will be presented to the same precision as the actual sampling time after dosing used for the calculation of PK parameters.

For all other data, means, medians and percentiles will be displayed to one more decimal place than the data, dispersion statistics (e.g. standard deviation) will have two more decimal places, and the minimum and maximum will be displayed to the same number of decimal places as reported in the raw data. Percentages will be displayed with one decimal place.

